15.4 Vital Signs

Vital signs data will be summarized by treatment and time point using descriptive statistics for baseline (see definition in Section 9), each evaluation during the study, and change from baseline to each evaluation. Listings of vital sign data will be provided.

Vital sign summaries will include all vital sign assessments from the on-treatment period. All vital sign assessments will be listed, and those collected outside the on-treatment period will be flagged in the listing.

15.5 Other Safety or Tolerability Evaluations

15.5.1 Standard Safety ECG

Standard safety ECG data include ventricular rate, PR interval, QRS duration, QT interval (uncorrected) and QTcB and QTcF and will be summarized by treatment and time point using descriptive statistics for baseline (see definition in Section 9). A listing of safety ECG data will be provided.

Safety standard ECG summaries will include all ECG assessments from the on-treatment period. All ECG assessments will be listed.

Investigator-reported interpretation safety standard ECG results will also be tabulated by study intervention and time point using the number and percentage of participants for each interpretation category (Normal, Abnormal Not Clinically Significant [NCS], Abnormal Clinically Significant [CS]). Abnormality reason will be listed.

16 Analyses of Other Endpoints

16.1 Pharmacokinetics

PK evaluation will be performed by Nuvisan GmbH.

All statistical analyses and descriptive summaries of PK data will be performed on the PK Analysis Set.

16.1.1 Descriptive Statistics of PK Concentration Data

PK measurements of evobrutinib [REDACTED] as well as moxifloxacin will be descriptively summarized using: number of non-missing observations (n), arithmetic mean (Mean), SD, coefficient of variation (CV%), minimum (Min), median (Median) and maximum (Max).

Descriptive statistics will only be calculated for $n > 2$ in which a measurement of BLQ represents a valid measurement and will be taken as zero for summary statistics of PK concentration data.

Any mean or median value that is below the lower limit of quantification will be shown as BLQ.

Descriptive statistics of PK concentration data will be calculated using values with the same precision as the source data and rounded for reporting purposes only. In export datasets, as well as in the SDTM PC domain, PK concentrations will be provided with full precision and will not be rounded.

The following conventions will be applied when reporting descriptive statistics of PK concentration data:

| | |
|-------------------------|----------------------|
| n | 0 decimal place |
| Mean, Min, Median, Max: | 3 significant digits |
| SD: | 4 significant digits |
| CV%: | 1 decimal place |

16.1.2 Descriptive Statistics of PK Parameter Data

PK parameter data of each analyte will be summarized using: number of non-missing observations (n), arithmetic mean (Mean), SD, coefficient of variation (CV%), minimum (Min), median (Median), maximum (Max), geometric mean (GeoMean), the geometric coefficient of variation (GeoCV) and the 95% confidence interval for the GeoMean (LCI 95% GM, UCI 95% GM). For PK parameters related to time (e.g. t_{max} , t_{lag} , t_{last}), only n, Min, Median, and Max may be reported.

Descriptive statistics will only be calculated for a PK parameter when $n > 2$.

PK parameters read directly from the measurements (i.e., C_{max}) will be reported with the same precision as the source data. All other PK parameters will be reported to 3 significant figures. In export datasets, as well as in the SDTM PP domain, PK parameters will be provided with full precision and will not be rounded. Descriptive statistics of PK parameter data will be calculated using full precision values and rounded for reporting purposes only.

The following conventions will be applied when reporting descriptive statistics of PK parameter data:

| | |
|--|----------------------|
| n | 0 decimal place |
| Mean, Min, Median, Max, GeoMean, 95% CI: | 3 significant digits |
| SD: | 4 significant digits |
| CV%, GeoCV%: | 1 decimal place |

16.1.3 Statistical Analysis of PK Parameter Data

Analysis of Primary Endpoints

All PK parameters will be analyzed descriptively as described above.

16.1.4 General Specifications for PK Concentration and PK Parameter Data

Predose samples that occur before the first drug administration will be assigned a time of 0 hours, as if the sample had been taken simultaneously with the study intervention administration. Same applies to the predose sample after multiple doses.

Predose or trough samples which have been taken after the subsequent dosing will be reported as a protocol deviation. The resulting concentrations will be included in concentration listings but excluded from descriptive statistics of concentrations and from PK parameter estimation.

Values BLQ will be taken as zero for summary statistics of PK concentration data, PK parameter estimation (e.g., AUC) and for graphical presentations.

Missing concentrations (e.g., no sample, insufficient sample volume for analysis, no result or result not valid) will be reported generally as "N.R.". A participant who withdraws prior to the last planned observation will be included in the analyses up to the time of discontinuation if still included in the PK analysis set.

If samples are collected outside the PK sampling time windows defined in the CSP in Section 8.4, these will be included in the PK parameter estimation (NCA) but will be excluded from the concentration summary and mean/median concentration plots.

PK concentrations which are erroneous due to a sampling processing or analytical error (as documented in the bioanalytical report) may be excluded from the PK analysis if agreed by the Sponsor. In this case the rationale for exclusion will be provided in the CSR. Any other PK concentrations that appear implausible to the Clinical Pharmacologist/Clinical PK/PD Scientist will not be excluded from the analysis. Any implausible data will be documented in the CSR.

If important protocol deviations occurred likely to affect the PK profile of participants as specified in Section 10.2.1, the impacted concentrations and PK parameters will be excluded from summary statistics and further statistical evaluation.

Any PK concentrations or PK parameters excluded from summary statistics will be included in participants listings and flagged; a reason for exclusion will be detailed in the CSR (e.g., a footnote or a table of exclusions). Any flags will be included in the study specific CDISC data sets.

PK concentrations and PK parameters excluded from summary statistics will not be included in mean/median figures. Mean plots will only contain values where $n > 2$.

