Triplicate ECGs from Holter recordings			X	X		X	X		X	X		X	X		On each dosing day 12-lead ECGs extracted in triplicates from Holter recordings at 3 timepoints before dosing (-1 h, -30 min, and -10 min), and at 15 and 30 min and 1, 1.5, 2, 2.5 3, 4, 6, 8, 12, 16 h and at 24 h postdose.
Clinical laboratory safety tests	X	X			X			X			X		X		Blood samples for the clinical laboratory safety assessments will be collected in a fasted condition.
PK sampling (evobrutinib, evobrutinib major metabolite, and moxifloxacin)			X	X		X	X		X	X		X	X		Plasma samples for PK analysis will be collected on the days of dosing (i.e., Days 1, 8, 15, and 22) at predose and 15 and 30 min, and 1, 1.5, 2, 2.5, 3, 4, 6, 8, 12, 16 and 24 h postdose. At visits where assessment time points coincide with each other, the following sequence of activities will be followed: PK sample to be collected shortly (within time windows specified) after ECG.
Study intervention administration			X			X			X			X			
Previous/concomitant medication monitoring	X	<=====>													Section 6.8.
AE monitoring	X	<=====>													Section 8.3.

CRU=clinical research unit; ECG=electrocardiogram; eGFR=estimated glomerular filtration rate; FSH=follicle stimulating hormone; PK=pharmacokinetics; SARS-CoV-2=severe acute respiratory syndrome coronavirus 2; TSH=thyroid stimulating hormone.

2

[figure not shown]
Introduction

Evobrutinib is an oral, selective, irreversible inhibitor of BTK that is in clinical development for the treatment of autoimmune diseases, e.g. RMS. Detailed information on the chemistry, pharmacology, efficacy, and safety of evobrutinib is in the current IB.

This study is being conducted to assess potential effects of evobrutinib on cardiac repolarization (i.e., prolongation of QT interval).

CC1

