2.2 Background

Evobrutinib

Evobrutinib (also known as M2951 and MSC2364447C) is an oral, selective, irreversible inhibitor of BTK. Evobrutinib inhibits primary B cell responses, such as proliferation and antibody and cytokine release, without directly affecting T cells. Indirect effects on T cells can be mediated by BTK inhibition by blocking the B cell antigen presentation function. In addition, BTK inhibition

blocks the activation of innate immune cells by immune complexes downstream of Fc receptor activation. All 3 mechanisms may play a role in the pathogenesis of various autoimmune diseases. Thus, BTK inhibition could provide clinical benefit in the treatment of multiple autoimmune diseases including RMS.

In clinical studies with healthy participants, evobrutinib was rapidly absorbed with a t_{max} of 0.5 to 1.5 hours under fasted conditions. Evobrutinib demonstrated dose-proportional PK (i.e. C_{max} and $AUC_{0-\infty}$) over the evaluated dose range of 25 to 500 mg single dose and 25 to 200 mg once daily multiple dose. Median $t_{1/2}$ was approximately 2 hours (range 1.8 to 2.6 hours) at relevant plasma concentrations following a single oral dose of 25 to 200 mg. Accumulation of evobrutinib is minimal with daily dosing (refer to IB).

Moxifloxacin

Moxifloxacin 400 mg film-coated tablets are indicated for the treatment of bacterial infections in patients 18 years and older caused by bacteria susceptible to moxifloxacin. Following oral administration, moxifloxacin is rapidly and almost completely absorbed. The absolute bioavailability is approximately 91%. Its pharmacokinetics are linear in the range of 50 to 800 mg single dose and up to 600 mg once daily dosing over 10 days. Following a 400 mg oral dose, peak concentrations of 3.1 mg/L are reached within 0.5 to 4 h after dosing. Moxifloxacin is frequently used in thorough QT studies as a positive control because it induces small and consistent prolongations of QT/QTc but is not considered as having a proarrhythmic activity (refer to moxifloxacin approved product information).

QT Interval

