16.1.5.1 Estimation of Pharmacokinetic Parameters in Plasma

PK parameters will be calculated using the actual elapsed time since dosing. If the actual sampling time is missing, calculations may be performed using the scheduled time. Details (e.g., number of samples, participants affected) will be described in the CSR. If actual dosing time is missing, scheduled time might be used for NCA after performance of adequate plausibility checks and agreement with the sponsor. Decision and rational should be included in the CSR. Otherwise, there will be no further imputation of missing data.

The following PK parameters will be calculated, when appropriate: PK parameters will be calculated for all analytes and unless otherwise noted.

| Symbol | Definition |
|-----------------------------------|---|
| AUC ₀₋₂₄ | The partial AUC from time zero (= dosing time) to 24 hours. |
| AUC _{0-t_{last}} | The AUC from time zero (= dosing time) to the time of the last quantifiable concentration (t _{last}). |
| AUC _{0-∞} | The AUC from time zero (= dosing time) up to infinity with extrapolation of the terminal phase. |
| AUCextra% | The AUC from time t _{last} extrapolated to infinity given as percentage of AUC _{0-∞} . |
| C _{max} | Maximum observed concentration. |
| CL/F | The apparent total body clearance following extravascular administration (parent only). |
| λ _z | Terminal first order (elimination) rate constant. |
| t _{max} | The time to reach the C _{max} in a dosing interval. |
| t _{1/2} | The terminal half-life. |
| V _{z/F} | The apparent volume of distribution during the terminal phase following extravascular administration (parent only). |

Additional PK parameters may be calculated where appropriate.

Units for PK parameter outputs will be based on concentration and dose units used in the study, unless otherwise specified. If concentration data units change within the study, PK parameters will be reported using consistent units throughout study outputs. In such cases, the Sponsor will specify relevant units for reporting before the final PK evaluation.

The parameters C_{max} and t_{max} will be obtained directly from the concentration-time profiles. If C_{max} occurs at more than one timepoint, t_{max} will be assigned to the first occurrence of C_{max}.

The following PK parameters will be calculated for diagnostic purposes and listed, but will not be summarized:

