- First (λ_z low) and last (λ_z up) time point of the time interval of the log-linear regression to determine λ_z.
- Number of data points (Nλ) included in the log-linear regression analysis to determine λ_z.
- Goodness of fit statistic (adjusted Rsq) for calculation of λ_z.
- AUC from time t_{last} extrapolated to infinity given as percentage of AUC_{0-∞}. (AUC_{extra%})
- Span ratio of interval over which t_{1/2} was estimated/t_{1/2}

The regression analysis should contain data from at least 3 different time points in the terminal phase consistent with the assessment of a straight line on the log-transformed scale. Phoenix WinNonlin "best fit" methodology will be used as standard. If warranted, further adjustment may be made by the pharmacokineticist, after agreement with the Sponsor. The last quantifiable concentration > LLOQ should always be included in the regression analysis, while the concentration at t_{max} and any concentrations BLQ which occur after the last quantifiable data point > LLOQ should not be used.

If AUC_{extra%}> 20% and/or the coefficient of correlation (Rsq adj) of λ_z is < 0.8 and/or the observation period over which the regression line is estimated (span ratio) is less than 2-fold the resulting t_{1/2}, the rate constants and all derived parameters (e.g. t_{1/2}, AUC_{0-∞}, CL/F, etc.) will be

listed, flagged and included in the parameter outputs. Should more than 10% of subjects be flagged for AUCextra and/or Rsq adj (for a particular analyte), a sensitivity analysis excluding flagged parameters may be performed after discussion with the Sponsor.

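### Setting below-quantification samples to zero for AUC gives AUC0-24 and AUC0-∞ inconsistent tails; with tlast at 16 h and a half-life below about 2.8 h, the partial area exceeds the total

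*SAP*

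**What the plan says.** AUC0-24 and AUC0-∞ are both named as secondary endpoints for evobrutinib, its major metabolite and moxifloxacin (Protocol 3; SAP 5). SAP 16.1.5.1 defines the first as "The partial AUC from time zero (= dosing time) to 24 hours". The second runs "up to infinity with extrapolation of the terminal phase".

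The general rule for BLQ values is in SAP 16.1.4: "Values BLQ will be taken as zero for summary statistics of PK concentration data, PK parameter estimation (e.g., AUC) and for graphical presentations". It names AUC and does not separate samples before the first quantifiable concentration from samples after the last.

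SAP 16.1.5.1 does make an exception for trailing values, but only for the regression that estimates λz: "any concentrations BLQ which occur after the last quantifiable data point > LLOQ should not be used". Neither section names a trapezoidal rule or says how AUC0-24 is completed when tlast falls before 24 h.

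Two facts from the protocol fix the size of the effect. Section 1.3 schedules PK samples "at predose and 15 and 30 min, and 1, 1.5, 2, 2.5, 3, 4, 6, 8, 12, 16 and 24 h postdose". Section 2.2 says that the median evobrutinib half-life "was approximately 2 hours (range 1.8 to 2.6 hours) at relevant plasma concentrations following a single oral dose of 25 to 200 mg".

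**The concern.** With a half-life near 2 h, 24 h is about 12 half-lives after dosing, so many evobrutinib profiles may be BLQ before the last sample. AUC0-24 then has to be carried past tlast. A zero at the next sampling time replaces the exponential tail by a triangle whose area depends on the gap between samples and not on the drug's elimination. AUC0-∞ for the same profile ignores those zeros and uses Clast/λz.

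The two endpoints therefore rest on different tails. When the gap is wide, as between 16 and 24 h, the triangle can be larger than the whole tail to infinity, so that a part exceeds the total. When the gap is 4 h, the triangle is too small. SAP 16.1.2 sends unrounded parameters to the SDTM PP domain, so an impossible ordering would be visible there even where rounding hides it in tables.

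**Working it through.** The plan states no AUC figure to reproduce. The check compares the tails after tlast in units of Clast, then scales them to total AUC.

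**Inputs.** Sampling at 8, 12, 16 and 24 h (Protocol 1.3). Half-life (t½) 1.8, 2.0 and 2.6 h (Protocol 2.2). Actual times are used in the noncompartmental analysis (SAP 16.1.5.1). The windows at 16 and 24 h are ±15 min (Protocol 8.4.1, Table 1).

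**Formulas**, with g the gap to the next sample:
- triangle to a zero: g/2;
- tail to infinity: 1/λz = t½/ln 2;
- λz tail to 24 h: (t½/ln 2) × (1 − 2^(−(24 − tlast)/t½)).

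A log-trapezoidal step cannot run to zero, so linear and linear-up/log-down rules give the same triangle.

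**tlast = 16 h** (g = 8 h, triangle 4.0 × Clast):

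| t½ (h) | Tail to infinity | λz tail to 24 h | Triangle |
|---|---|---|---|
| 1.8 | 2.60 | 2.48 | 4.0 |
| 2.0 | 2.89 | 2.71 | 4.0 |
| 2.6 | 3.75 | 3.31 | 4.0 |

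The triangle exceeds the tail to infinity when g/2 > t½/ln 2, that is when t½ < 4 × ln 2 = 2.77 h. The windows allow a gap of 7.5 to 8.5 h, which moves the cut-off to 3.75 × ln 2 = 2.60 h and 4.25 × ln 2 = 2.95 h. This step needs no assumption about absorption or the quantification limit.

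**tlast = 12 or 8 h** (g = 4 h): the triangle is 2.0 × Clast. This is below the λz tail to 24 h at every half-life listed. For example, at t½ 2.0 h that tail is 2.84 × Clast from 12 h and 2.87 × Clast from 8 h.

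**Size relative to total AUC.** Assume a one-compartment oral model with absorption rate ka. For t½ 2.0 h and ka 4/h, λz = 0.3466 and ka/(ka − λz) = 1.095. In units of dose/volume, total AUC = 1/λz = 2.885.
- C16 = 1.095 × 2^−8 = 0.00428. Excess of AUC0-24 over AUC0-∞ = (4.0 − 2.885) × 0.00428 / 2.885 = 0.17%. Against the λz-completed AUC0-24: (4.0 − 2.705) × 0.00428 / 2.885 = 0.19% too high.
- C12 = 1.095 × 2^−6 = 0.0171. Error = (2.0 − 2.84) × 0.0171 / 2.885 = −0.50%.
- C8 = 1.095 × 2^−4 = 0.0684. Error = (2.0 − 2.87) × 0.0684 / 2.885 = −2.1%.

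Running the same model on the protocol's sampling grid with t½ 1.8 to 2.6 h and ka 1.5 to 8/h gives:

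| tlast | AUC0-24 against AUC0-∞ | AUC0-24 against λz-completed AUC0-24 |
|---|---|---|
| 16 h | +0.1% to +0.2% | +0.1% to +0.3% |
| 12 h | below | −0.2% to about −2% |
| 8 h | below | −1% to about −7% |

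The shortfall at an early tlast is thus larger than the excess at 16 h.

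**The case against.** **The mechanism is inferred.** The SAP does not say that AUC0-24 is integrated down to the zero. That is fair. But the rule assigns zero to BLQ values for parameter estimation and names AUC, so integrating to the zero is what the text most naturally asks for. The only exception for trailing values is confined to the λz regression.

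**Not every profile with tlast at 16 h inverts.** A reader might infer that all of them do. The documents do not support that. The order reverses above 2.77 h, and within the sampling windows the cut-off can be as low as 2.60 h, the top of the documented range. That range accompanies a median, refers to relevant plasma concentrations and covers 25 to 200 mg. It does not bound individual terminal half-lives, and 225 mg lies outside it. If individual half-lives were log-normal with median 2.0 h and a CV of 15% to 30% (assumed), about 1% to 13% would exceed 2.77 h. Profiles still quantifiable at 16 h are likely to be the slower ones.

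**Frequency is unknown.** In the model, tlast at 16 h needs a quantification limit between the 24 h level (about 0.01% to 0.3% of Cmax) and the 16 h level (about 0.3% to 2.6% of Cmax). The documents give no limit, and no half-life for the metabolite. This stands.

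**Nothing inferential depends on it.** A reader might argue that the error distorts the comparison of 45 mg with 225 mg, because tlast tends to be earlier at the lower dose. The direction is plausible, but SAP 16.1.3 analyses all PK parameters descriptively and plans no between-dose comparison. The concentration-QTc analysis uses matched concentrations and moxifloxacin assay sensitivity uses Cmax; neither uses AUC. An excess of 0.1% to 0.2% will often disappear at the three significant figures that SAP 16.1.2 reports. All of this stands and limits the point to a minor one.

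**Conclusion.** The point holds as a minor defect of specification. A stated rule, read naturally, gives two named secondary endpoints inconsistent tails for the same profile. With tlast at 16 h and a half-life below about 2.8 h, it produces a partial AUC above the total AUC.

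That inversion follows from the sampling times and the half-life alone. The percentages rest on a one-compartment model with assumed absorption and on half-lives of 1.8 to 2.6 h. How many profiles fall into each case cannot be told from the documents, and nothing can be shown for the metabolite. No conclusion about QTc changes.

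**What to change.** In SAP 16.1.4, keep zero for concentration summaries and for BLQ values before the first quantifiable sample. For AUC, treat BLQ values after tlast as missing. Compute AUC0-24 as AUC0-tlast plus the λz-extrapolated area from tlast to 24 h; where λz cannot be estimated, report AUC0-tlast with a flag.

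With this rule the tail at tlast 16 h is 2.48, 2.71 and 3.31 × Clast at half-lives of 1.8, 2.0 and 2.6 h, each below the corresponding tail to infinity. In general the factor 1 − 2^(−(24 − tlast)/t½) is below 1, so the inversion cannot occur.

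The cost is about a sentence in the SAP and a software setting before database lock, with no new data. The drawback is that AUC0-24 then depends on the λz estimate, as AUC0-∞ already does.

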16.1.5 Estimation of Pharmacokinetic Parameters

The computer program Phoenix® WinNonlin® version 6.4, or higher (Certara, L.P., [name]) will be used to derive PK parameters applying NCA.

The statistical software SAS® (Statistical Analysis System, SAS-Institute, Cary NC, USA, windows version 9.1 or higher) will be used to generate additional PK parameters and produce tables, listings, and figures.

16.1.5.1 Estimation of Pharmacokinetic Parameters in Plasma

PK parameters will be calculated using the actual elapsed time since dosing. If the actual sampling time is missing, calculations may be performed using the scheduled time. Details (e.g., number of samples, participants affected) will be described in the CSR. If actual dosing time is missing, scheduled time might be used for NCA after performance of adequate plausibility checks and agreement with the sponsor. Decision and rational should be included in the CSR. Otherwise, there will be no further imputation of missing data.

The following PK parameters will be calculated, when appropriate: PK parameters will be calculated for all analytes and unless otherwise noted.

| Symbol | Definition |
|-----------------------------------|---|
| AUC ₀₋₂₄ | The partial AUC from time zero (= dosing time) to 24 hours. |
| AUC _{0-t_{last}} | The AUC from time zero (= dosing time) to the time of the last quantifiable concentration (t _{last}). |
| AUC _{0-∞} | The AUC from time zero (= dosing time) up to infinity with extrapolation of the terminal phase. |
| AUCextra% | The AUC from time t _{last} extrapolated to infinity given as percentage of AUC _{0-∞} . |
| C _{max} | Maximum observed concentration. |
| CL/F | The apparent total body clearance following extravascular administration (parent only). |
| λ _z | Terminal first order (elimination) rate constant. |
| t _{max} | The time to reach the C _{max} in a dosing interval. |
| t _{1/2} | The terminal half-life. |
| V _{z/F} | The apparent volume of distribution during the terminal phase following extravascular administration (parent only). |

Additional PK parameters may be calculated where appropriate.

Units for PK parameter outputs will be based on concentration and dose units used in the study, unless otherwise specified. If concentration data units change within the study, PK parameters will be reported using consistent units throughout study outputs. In such cases, the Sponsor will specify relevant units for reporting before the final PK evaluation.

The parameters C_{max} and t_{max} will be obtained directly from the concentration-time profiles. If C_{max} occurs at more than one timepoint, t_{max} will be assigned to the first occurrence of C_{max}.

The following PK parameters will be calculated for diagnostic purposes and listed, but will not be summarized:

- First (λ_z low) and last (λ_z up) time point of the time interval of the log-linear regression to determine λ_z.
- Number of data points (Nλ) included in the log-linear regression analysis to determine λ_z.
- Goodness of fit statistic (adjusted Rsq) for calculation of λ_z.
- AUC from time t_{last} extrapolated to infinity given as percentage of AUC_{0-∞}. (AUC_{extra%})
- Span ratio of interval over which t_{1/2} was estimated/t_{1/2}

The regression analysis should contain data from at least 3 different time points in the terminal phase consistent with the assessment of a straight line on the log-transformed scale. Phoenix WinNonlin "best fit" methodology will be used as standard. If warranted, further adjustment may be made by the pharmacokineticist, after agreement with the Sponsor. The last quantifiable concentration > LLOQ should always be included in the regression analysis, while the concentration at t_{max} and any concentrations BLQ which occur after the last quantifiable data point > LLOQ should not be used.

If AUC_{extra%}> 20% and/or the coefficient of correlation (Rsq adj) of λ_z is < 0.8 and/or the observation period over which the regression line is estimated (span ratio) is less than 2-fold the resulting t_{1/2}, the rate constants and all derived parameters (e.g. t_{1/2}, AUC_{0-∞}, CL/F, etc.) will be

listed, flagged and included in the parameter outputs. Should more than 10% of subjects be flagged for AUCextra and/or Rsq adj (for a particular analyte), a sensitivity analysis excluding flagged parameters may be performed after discussion with the Sponsor.

